STUDY ID: NCT02779491.

EVALUATION OF A 5-A-DAY FRUIT AND VEGETABLE MOBILE PHONE APPLICATION

STUDY PROTOCOL AND STATISTICAL ANALYSIS PLAN

DOCUMENT DATE: 15.04.19

METHODS

Evaluation of the app was undertaken using a randomized controlled pilot trial, where volunteers were randomized to receive or not receive the app for either two weeks or four weeks and FV knowledge, FV intake and FV behaviour were assessed and compared at baseline and at study end.

Volunteers

Volunteers to test the app were recruited from the staff and students of Bournemouth University, UK, from Nov., 2015 to March, 2017. We aimed to recruit 100 volunteers - 50 to test the app and 50 to act as controls. No earlier research was available to allow power calculations, thus 50 volunteers were considered sufficient to gain feedback and assess potential impacts of the app, while remaining manageable should few impacts be found. Adult volunteers (aged 18 years and over) were required to own an Android smart phone, as the app was only developed for Android platforms, but there were no other inclusion / exclusion criteria to maximise the generalisability of the study. Volunteers were recruited for a study to 'test a novel mobile phone app for encouraging healthy behaviours'. Volunteers were thus aware at the study start, that they may or may not receive an app to test, but they were informed that that the app may target one of a number of health behaviours, such as exercising, stress reduction or healthy eating.

Intervention / Control

Volunteers were randomized to receive the app (intervention) or not receive the app (control). Randomization was undertaken on study entry by drawing lots, and recruitment stopped once 50 individuals had been randomized to test the app. All volunteers who received the app were asked to download the app onto their phones, to register with the app to set-up a user profile, and to use the app as often as they wished for either a two week or a four week period. The app was tested for two weeks from Nov. 2015 - March 2016 and from Nov. 2016 - March 2017, and for four weeks from June 2016 - August 2016.

Outcomes

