Awareness of the 5-a-day FV recommendations, FV knowledge and FV intake were assessed as outcomes, at baseline, at a mid point, and at study end. Awareness of the recommendations, FV knowledge and self-reported FV intakes were assessed using a questionnaire previously developed by ourselves [1]. The questionnaire consisted of two questions on awareness of the 5-a-day message, four questions on knowledge of the details of the message (which foods are included, portion sizes, the need for variety, reasons for consumption), and two questions on FV intake, as

detailed below. FV behaviour was also assessed as part of the trial using a behavioural measure. Two questions on demographic and lifestyle characteristics that have previously been associated with FV consumption and dietary knowledge [1-9] were also assessed as potential confounders. All volunteers (intervention and control) completed all outcome assessments in the same manner.

Awareness of the recommendations: Awareness of the recommendations were assessed using two open-response questions: 'Are you aware of the 5-a-day FV message?' and 'What do you think it means?'

FV knowledge: FV knowledge was assessed using four structured closed-response questions on: 1) the FV that are included in the message; 2) the portion sizes that are required for the message; 3) the variety that is required for the message; and 4) the reasons for FV consumption. These questions include 1) a number of foods; 2) a number of different portions of FV; 3) a number of combinations of FV to be consumed in a day; and 4) a number of different health conditions, respectively, and respondents were asked to report 1) inclusion in the recommendations or not; 2) contribution to the recommendations based on portion sizes; 3) number of FV portions consumed in the day; and 4) impact of FV on each health condition, respectively. For all questions, a correct response, based on current recommendations from the UK Government [10], was scored +1, an incorrect response was scored -1, and 'don't know / not sure' was scored 0. Missing values were also completed with 0, where found.

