The study was given ethical approval by the Research Ethics Committee of Bournemouth University, prior to commencement, and was registered as a clinical trial on www.clinicaltrials.gov (ID NCT02779491). Methods were undertaken as detailed in the trial registration with the exception that a behavioural measure of FV intake was added to the study prior to commencement, and a measure of FV attitudes was not undertaken. Attitudes towards FV were not measured to reduce demand characteristics given the extensive FV knowledge questionnaire. All participants provided written informed prior to starting the study.

Analysis: Data were analysed on an Intention-to-Treat basis, where missing data were completed using Last Observation Carried Forward. Demographic and lifestyle variables and all measures at baseline were first described and compared using t-tests, based on study duration and app / control

grouping. Several important differences were found between those studied for two weeks and those studied for four weeks, thus study duration was included in all subsequent analyses. All FV knowledge and intake outcome assessed by questionnaire were analysed using 2 (study duration) x 2 (app / control) x 2 (baseline / study end) mixed ANOVA. Our behavioural measure of FV intake – choice of fruit drink or non-fruit drink was analysed using Chi-squared tests. All data are reported as means and standard deviations. Significance was set at p<0.05.

REFERENCES

- 4. Ashfield-Watt PAL. Fruit and vegetables, 5+ a day: are we getting the message across? Asia Pac J Clin Nutr. 2006;15:245-52.

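### Smoothie choice: one study-end app/control comparison stratified by duration and baseline choice would be a cheap improvement on unspecified chi-squared tests

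*Combined protocol and SAP*

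**What the plan says.** The Analysis paragraph gives the drink outcome one clause: "choice of fruit drink or non-fruit drink was analysed using Chi-squared tests". It gives no table layout, time point or stratification. Just before, having found differences between the two-week and four-week cohorts, it says "thus study duration was included in all subsequent analyses". The outcomes assessed by questionnaire get a "2 (study duration) x 2 (app / control) x 2 (baseline / study end) mixed ANOVA"; that model is not extended to drink choice. The missing-data rule is general: "Data were analysed on an Intention-to-Treat basis, where missing data were completed using Last Observation Carried Forward".

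The opening of Methods says that "FV intake and FV behaviour were assessed and compared at baseline and at study end". Under Outcomes, assessments took place "at baseline, at a mid point, and at study end", and under Procedure a drink was offered on every assessment occasion, so each volunteer assessed at baseline had a baseline choice. Under FV Behaviour, the smoothie counts as an FV choice and the other drinks do not. Declining a drink was allowed, but its coding is not stated.

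Two facts bear on the remedy. The four-week cohort was a separate calendar block ("and for four weeks from June 2016 - August 2016"). The document was written after recruitment ended in March 2017 ("DOCUMENT DATE: 15.04.19").

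**The concern.** Smoothie choice is the only measure of FV intake in the trial that is not self-reported. The questionnaire outcomes have one model that brings together arm, duration and the baseline value. The behavioural outcome has only the name of a family of tests. The plural could cover tables by duration, tables of change, McNemar tests or a CMH test. These answer different questions, and a reader cannot tell which result is the app effect.

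A plain arm-by-choice table at study end uses neither duration nor baseline choice. If people tend to pick the same drink each time, leaving out baseline choice gives up precision that the data could supply at no extra collection cost. The instruction to report all data as means and standard deviations also does not suit a yes/no outcome.

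**Working it through.** The plan has no figure to reproduce: it says no power calculation was possible and gives no smoothie rate, cohort size or repeatability.

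**Inputs from the documents.** Target of 50 app and 50 control; significance at p<0.05; two cohorts; baseline and study-end choice both collected.

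**Assumed inputs.** Smoothie rate at study end, control vs app, 20% vs 40% or 30% vs 50%; baseline rate equal to the control rate; four-week share 25%, 33% or 50%; cohort shift 0, 0.5 or 1 latent SD; latent (tetrachoric) correlation between baseline and study-end choice from 0 to 0.8.

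**Starting point, unadjusted 2x2 test.** Power = Φ{[d - 1.96·√(2p̄(1-p̄)/n)] / √[(p1(1-p1) + p2(1-p2))/n]}, with d = 0.2 and n = 50.
- 20% vs 40%: (0.2 - 1.96 × 0.0917)/0.0894 = 0.228, power 0.59.
- 30% vs 50%: (0.2 - 1.96 × 0.0980)/0.0959 = 0.083, power 0.53.

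**Effect of adding baseline choice.** Latent-normal simulation, 100 volunteers, no missing data, 10,000 trials in each of 2 × 3 × 3 × 5 = 90 scenarios, Monte Carlo error about 0.5 points. The comparator is a CMH test by duration only, which already respects the plan's duration rule (power 53-66%).

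| Correlation | Change in power (points) | Separately coded simulation, four-week share 33% |
|---|---|---|
| 0 | -1.4 to -0.6 | -1.5 to -0.7 |
| 0.3 | -0.4 to +0.9 | -0.4 to +0.6 |
| 0.5 | +2.2 to +3.8 | +2.4 to +3.5 |
| 0.7 | +7.3 to +9.6 | +8.1 to +9.6 |
| 0.8 | +11.7 to +15.2 | +13.3 to +14.8 |

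Type I error of the test stratified by duration and baseline choice was 4.5-5.4%. For the pooled unadjusted test it was 4.4-5.8%, so both are valid.

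**Sensitivity to the model.** A random-intercept logistic simulation (app log odds ratio 1.0, 30% in the four-week cohort) compared the same stratified CMH test with the unadjusted test. Power was 0.66 vs 0.68, 0.43 vs 0.43 and 0.27 vs 0.22 at intercept SDs of 0, 1.5 and 3. The latent correlation is SD²/(SD² + π²/3), which gives 0, 2.25/5.54 = 0.41 and 9/12.29 = 0.73. The gain is therefore nil at moderate repeatability and 5 points at high repeatability under that model.

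**Hand-checkable illustration (invented counts, smoothie/total).**

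| Stratum | App | Control | Observed - expected (app) | Variance |
|---|---|---|---|---|
| Two-week, baseline no | 7/24 | 3/24 | 7 - 5 = 2 | 2.021 |
| Two-week, baseline yes | 7/9 | 5/9 | 7 - 6 = 1 | 1.059 |
| Four-week, baseline no | 4/11 | 2/11 | 4 - 3 = 1 | 1.143 |
| Four-week, baseline yes | 5/6 | 5/6 | 5 - 5 = 0 | 0.455 |

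Each variance is n1·n0·t(N-t)/[N²(N-1)], where t is the number choosing a smoothie in the stratum.
- Pooled, 23/50 vs 15/50: 100 × (23×35 - 27×15)²/(50×50×38×62) = 2.72, p = 0.099.
- CMH by duration (14/33 vs 8/33; 9/17 vs 7/17): (3 + 1)²/(3.723 + 2.182) = 2.71, p = 0.100.
- CMH by duration and baseline: 4²/4.678 = 3.42, p = 0.064. The Mantel-Haenszel odds ratio is 6.671/2.671 = 2.50 (95% CI 0.95 to 6.57).

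**The case against.** The strongest reply is that this is mainly a gap in description. The general sentence on duration precedes the chi-squared sentence and covers it, so only the mechanism is missing. Methods says behaviour was compared at both time points, so use of baseline is not ruled out. The trial is a pilot without a power calculation, and a few points of power on one outcome matter little. The repeatability that drives the gain is unknown. Four strata in about 100 people are thin. Nothing done now can be pre-specified. All of this stands, and it limits the point to a cheap improvement.

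A reader might infer more, and the documents do not support it:
- **Duration was ignored, or a wrong test was run.** The text says duration was included, and it does not show which tables were tested.
- **The unadjusted result is invalid.** Arm was drawn by lot on entry, so a study-end comparison between arms is valid without adjustment.
- **The false-positive rate is about 10%.** The figure 1 - 0.95² = 0.0975 needs two separate tests by duration, each read as the answer. The plan does not say this was done.
- **The gain is much larger.** Bigger figures arise against a pooled test, against a two-degree-of-freedom table of change, or with an assumed 20% missing. The plan does not commit to either analysis or give a missing rate. Part of the gain under carry-forward is mechanical, because a baseline choice carried forward equals the stratifying variable.
- **Volunteers who declined a drink were dropped.** The Intention-to-Treat sentence weighs against that. What is open is whether no drink was coded non-FV or treated as missing and carried forward.

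**Conclusion.** The point holds as an inexpensive gain in efficiency and clarity. The plan names no app/control comparison of smoothie choice that uses the baseline choice, although that choice was collected and the questionnaire outcomes use their baseline values.

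Against a test that already stratifies by duration, the expected change in power runs from a loss of 1 to 2 points when baseline choice is uninformative to a gain of 12 to 15 points at a correlation of 0.8. Up to 0.3 it is negligible. These figures rest on 50 per arm, the two assumed rate pairs and a latent-normal model; the logistic model gave smaller gains. The actual number of controls may also differ from 50, since recruitment stopped on the app count. The benefit that does not depend on repeatability is one defined answer for the trial's only intake measure that is not self-reported.

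**What to change.** Add to the Analysis paragraph, labelled post hoc:
- Compare study-end choice (smoothie versus everything else, with no drink counted as non-FV) between app and control in one CMH test stratified by study duration and baseline choice.
- Report counts by arm and the common odds ratio with its 95% CI, in place of means and standard deviations.
- Show this beside the chi-squared tests already run, stating which tables those tests used and how duration entered them.
- State that the mid-point choice is used only where it is carried forward.

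Logistic regression on arm, duration and baseline choice would be an acceptable alternative.

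The cost is a few sentences and a short re-analysis of data in hand. There are two downsides. One is the loss of about 1 to 2 points of power if baseline choice does not predict. The other is sparse strata: the Mantel-Fleiss adequacy value reached 5 in 96-100% of simulated trials with an app effect, but in as few as 55% under some null scenarios without missing data. If that is a worry, fix the mid-p exact conditional method before the re-analysis is run, so that the choice does not depend on the result. It cost at most 0.9 points of power in simulation, against 3.3 to 5.7 for the ordinary exact test.

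### One unadjusted p<0.05 rule covers the knowledge, intake and drink-choice tests, and this document names no primary outcome, app contrast or multiplicity rule: a useless app would reach significance somewhere about 10–30% of the time

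*Combined protocol and SAP*

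**What the plan says.** The opening of Methods states that "Evaluation of the app was undertaken using a randomized controlled pilot trial" and that "FV knowledge, FV intake and FV behaviour were assessed and compared at baseline and at study end". The Volunteers section gives no power calculation. It aims for 50 app users and 50 controls, and treats 50 as enough to obtain feedback and look for possible impacts.

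The Outcomes section lists awareness, knowledge and intake side by side and adds a drink-choice measure, with none ranked first. Knowledge comes from four questions, and the text does not say whether they are summed. Intake has two versions, calculated and estimated.

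On testing, the Analysis section says:

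- Questionnaire outcomes: "All FV knowledge and intake outcome assessed by questionnaire were analysed using 2 (study duration", with arm and time (baseline, study end) as the other two factors.
- Drink choice: "choice of fruit drink or non-fruit drink was analysed using Chi-squared tests". The number of tests is not given.
- Awareness: no test is stated.
- Threshold: "Significance was set at p<0.05".
- Reporting: "All data are reported as means and standard deviations". No between-arm difference or interval is mentioned.

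On the registration, the Procedure section says "Methods were undertaken as detailed in the trial registration", with two exceptions: "a behavioural measure of FV intake was added to the study prior to commencement", and attitudes were not measured.

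**The concern.** Several outcomes share one unqualified threshold. Nothing in this document tells the reader which result would count as the app working, or which ANOVA term carries it. A chance finding on any one outcome could then be reported as a significant impact of the app.

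There is a second, related cost. A pilot without a power calculation is most useful for showing how large the app effect might be and how uncertain that is. A significance rule with arm means and SDs does not give this directly. The natural app test in the stated ANOVA, app x time, also uses the baseline less efficiently than an adjusted comparison of the same data.

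**Working it through.** The plan gives no error rate or precision figure to reproduce, so the check starts from its test list.

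**Number of tests.** Because Methods describes a comparison of baseline with study end, app x time is taken as the app test. Questionnaire outcomes number 4 + 2 = 6 if the knowledge questions are tested separately, or 1 + 2 = 3 if they are summed. One drink test is assumed. That makes k = 7 or k = 4.

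**Independent tests, no app effect.** P(at least one p<0.05) = 1 − 0.95^k.

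- k = 4: 1 − 0.95^4 = 0.185
- k = 7: 1 − 0.95^7 = 0.302

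**Correlated tests.** The documents give no correlations, so these are assumed. Figures are from simulation of two-sided tests at 5%, with all tests, including the drink test, equally correlated.

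| Correlation | k = 4 | k = 7 |
|---|---|---|
| 0 | 18.5% | 30.1% |
| 0.3 | 17.3% | 27.2% |
| 0.5 | 15.5% | 22.9% |
| 0.7 | 13.0% | 17.9% |
| 0.9 | 9.4% | 11.3% |

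If the drink test is instead independent of the questionnaire outcomes, the figures at 0.7 are 15.5% and 20.6%. Including correlation with the drink test is reasonable, because the FV Behaviour section presents drink choice as another measure of intake. The overall range is therefore about 10–30%, or 9.4/5 = 1.9 to 30.2/5 = 6.0 times the nominal rate.

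Two readings would raise these figures and are left out of the range. Two drink tests would give 1 − 0.95^5 = 0.226 or 1 − 0.95^8 = 0.337 under independence. Also reading app x time x duration as an app effect would give about 23–30% (three outcomes) or 32–49% (six) at correlations 0 to 0.7.

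**Precision.** Inputs are 50 per group (the aim in Volunteers), equal variances at baseline and end, and an assumed baseline-to-end correlation r. The 95% CI half-widths in SD units, with t = 1.985 on 96 df and sqrt(1/50 + 1/50) = 0.2, are:

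- app x time (change): 1.985 × 0.2 × sqrt(2(1 − r))
- baseline-adjusted: 1.985 × 0.2 × sqrt(1 − r²)

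| r | App x time | Adjusted | Variance ratio (1 + r)/2 |
|---|---|---|---|
| 0.3 | 0.47 | 0.38 | 0.65 |
| 0.5 | 0.40 | 0.34 | 0.75 |
| 0.7 | 0.31 | 0.28 | 0.85 |

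At r = 0.5 the gain equals 1/0.75 = 1.33 times the participants. At r = 0.7 it is 1/0.85 = 1.18 times.

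The control count is not fixed, because recruitment stopped on reaching 50 app users. With 40 or 60 controls and r = 0.5, the half-width falls from 0.42 to 0.37 or from 0.38 to 0.33. The change figures assume that the two duration cohorts are weighted by size. Weighting unequal cohorts equally would widen them.

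**Drink choice.** 1.96 × sqrt(2p(1 − p)/50) = 0.157, 0.180 and 0.196 for assumed smoothie proportions of 0.2, 0.3 and 0.5. The half-width is thus about 16 to 20 percentage points.

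**The case against.** The strongest reply is that this is a pilot. It makes no confirmatory claim, so strict error control is partly a matter of preference. That stands as a reason not to demand a multiplicity-corrected confirmatory analysis. It does not excuse an unqualified threshold, because the document never calls its tests exploratory.

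Several stronger readings are tempting, and the documents do not support them:

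- **That the rule tests every listed outcome.** Awareness is listed as an outcome but has no stated test. The mid-point assessment is not in the ANOVA either, so the plan already limits its testing somewhat.
- **That the trial never had a primary outcome.** Only its absence from this document can be checked. If the registration names a single primary, most of the error-rate concern goes. The other tests would still carry the same unqualified p<0.05.
- **That the error rate is at least three times nominal.** That needs moderate correlations or an independent drink test. Four tests all correlated at 0.7 to 0.9 give 13.0% down to 9.4%.
- **That app x time is wrong.** It is a valid test of differential change, and the shortfall is in precision only. Last observation carried forward may raise the baseline-to-end correlation, which would shrink the gain: at r = 0.8 the half-width moves only from 0.25 to 0.24 SD.
- **That intervals are ruled out.** A short methods text that does not mention them does not exclude them. A reader with the group sizes could derive an unadjusted end-of-study difference and interval from the reported means and SDs.

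It is also fair to say that changing the model now is itself post hoc. Recruitment ended in March 2017, the document is dated April 2019, and the analysis is described in the past tense. The fix therefore has to disclose the change.

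**Conclusion.** The concern holds for the knowledge, questionnaire-intake and drink-choice tests. Followed as written, the rule gives an ineffective app about a 10–30% chance of at least one significant result. The size depends on whether knowledge is summed and on correlations that the documents do not give. It also rests on reading only app x time plus one drink test.

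The precision loss is real but moderate. It is 0.09, 0.05 or 0.02 SD in half-width at r = 0.3, 0.5 or 0.7 (unrounded 0.470 − 0.379, 0.397 − 0.344 and 0.308 − 0.284), for 50 per group. The point should be acted on, with medium confidence, because the pilot aim softens it and the registration could resolve part of it.

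**What to change.** - **Questionnaire outcomes.** Report the app-control difference at study end, adjusted for that outcome's baseline value and for study duration, with a 95% CI, as the estimate of the app effect. State that it replaces the app x time test after data collection, and keep the ANOVA result beside it.
- **Drink choice.** Report the difference in proportions at study end with a 95% CI, stratified by or adjusted for study duration, since the Analysis section carries duration into all later analyses.
- **Significance claims.** Reserve a claim at 0.05 for a primary outcome named in the registration, with Holm adjustment if it names more than one. Do not choose a primary now, as it would be post hoc.
- **Everything else.** Present the remaining results as exploratory estimates with intervals. If the registration names no primary, this applies to all results, in line with the pilot aim.

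The cost is one regression per questionnaire outcome, one comparison of proportions and revised reporting text, all on data already collected. The downside is that fewer results can be called significant, and none if no primary was registered.
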